10.2. Populations for Analyses

10.2.1. Study Participant Disposition

A detailed description of subject disposition will be provided at the end of the study.

10.2.2. Study Participant Characteristics

The subject's age, sex, weight, BMI, height, race/subrace, or other demographic characteristics will be recorded and summarized by treatment as well as overall.

10.3. Statistical Analyses

Statistical analysis of this study will be the responsibility of Eli Lilly and Company or its designee.

Pharmacokinetic analyses will be conducted on the full analysis set. This set includes all data from all subjects receiving a dose of LY3074828, with evaluable PK data, according to the treatment the subjects actually received. Safety analyses will be conducted for all subjects receiving a dose of LY3074828, whether or not they completed all protocol requirements.

Additional exploratory analyses of the data will be conducted as deemed appropriate. Study results may be pooled with the results of other studies for population PK analysis purposes to avoid issues with post-hoc analyses and incomplete disclosures of analyses.

No adjustments for multiple comparisons will be made.

10.3.1. Safety Analyses

10.3.1.1. Clinical Evaluation of Safety

All investigational product and protocol procedure AEs will be listed, and if the frequency of events allows, safety data will be summarized using descriptive methodology.

The incidence of symptoms for each treatment will be presented by severity and by association with investigational product as perceived by the investigator. Symptoms reported to occur prior to study entry will be distinguished from those reported as new or increased in severity during the study. Each symptom will be classified by the most suitable term from the medical regulatory dictionary.

The number of investigational product-related SAEs will be reported.

10.3.1.2. Statistical Evaluation of Safety

Safety parameters that will be assessed include safety laboratory parameters, vital signs, and ECG parameters. The parameters, and changes from baseline (predose) where appropriate, will be listed, and summarized using standard descriptive statistics. Additional analysis will be performed if warranted upon review of the data.

10.3.2. Pharmacokinetic Analyses

10.3.2.1. Pharmacokinetic Parameter Estimation

Pharmacokinetic parameter estimates for LY3074828 will be calculated by standard noncompartmental methods of analysis.

The primary parameters for analysis will be $AUC(0-\infty)$ and $AUC(0-t_{last})$ of LY3074828. The secondary parameters for analysis will be C_{max} and time to C_{max} (t_{max}) of LY3074828. Other noncompartmental parameters, such as $t_{1/2}$, apparent total body clearance of drug calculated after extra-vascular administration (CL/F), and apparent volume of distribution at steady state after extra-vascular administration (V_z/F) may be reported.

The absolute bioavailability of LY3074828 will be calculated using $AUC(0-\infty)$ and $AUC(0-t_{last})$ values calculated after SC and IV administration of LY3074828.

10.3.2.2. Pharmacokinetic Statistical Inference

Pharmacokinetic parameter estimates will be evaluated to delineate effects of LY3074828 formulation when administered to healthy subjects by SC injection (Reference and Test SC 2 × 1-mL). Log-transformed C_{max} , $AUC(0-\infty)$, and $AUC(0-t_{last})$ estimates will be evaluated in a linear fixed-effect model with a fixed effect for formulation. The differences between the test (SC 2 × 1-mL) compared to the reference formulation will be back-transformed to present the ratios of geometric least squares means and the corresponding 90% CI.

The t_{max} will be analyzed using a Wilcoxon rank sum test. Estimates of the median difference, 90% CIs, and p-values from the Wilcoxon rank sum test will be calculated.

Similar analyses to those described above will be conducted to delineate the effect of administering the same volume as a single injection (SC $1 \times 2\text{-mL}$) or as 2 injections (SC $2 \times 1\text{-mL}$).

In order to evaluate absolute bioavailability, a fixed-effect model will be used to analyze the log-transformed $\text{AUC}(0-\infty)$ and $\text{AUC}(0-t_{\text{last}})$ of LY3074828. The model will contain formulation (SC or IV) as a fixed effect. The absolute bioavailability will be estimated for the ratio of the least-squares geometric means of the formulations (SC/IV). The corresponding 90% CI of the ratios will also be estimated. Data from Test IV will be used for the IV formulation (reference). If the number of injections is not observed to have an effect based on the analyses described above, data from SC $2 \times 1\text{-mL}$ and SC $1 \times 2\text{-mL}$ will be combined and used for the SC formulation (and will be considered the primary analysis). If the number of injections is observed to have an effect (ie, SC $2 \times 1\text{-mL}$ versus SC $1 \times 2\text{-mL}$), analyses to evaluate absolute bioavailability will be done separately (SC $2 \times 1\text{-mL}$ versus IV and SC $1 \times 2\text{-mL}$ versus IV). The primary analysis will be considered as that including SC $1 \times 2\text{-mL}$.

Where possible, a single linear model with contrasts to test the different objectives will be used. Additional analyses may be conducted if they are deemed appropriate.

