In order to evaluate absolute bioavailability, a fixed-effect model will be used to analyze the log-transformed $AUC(0-\infty)$ and $AUC(0-t_{\text{last}})$ of LY3074828. The model will contain formulation (SC or IV) as a fixed effect. The absolute bioavailability will be estimated for the ratio of the least-squares geometric means of the formulations (SC/IV). The corresponding 90% CI of the ratios will also be estimated. Data from Test IV will be used for the IV formulation (reference). If the number of injections is not observed to have an effect based on the analyses described above, data from SC $2 \times 1\text{-mL}$ and SC $1 \times 2\text{-mL}$ will be combined and used for the SC formulation (and will be considered the primary analysis). If the number of injections is observed to have an effect (SC $2 \times 1\text{-mL}$ versus SC $1 \times 2\text{-mL}$ comparison), analyses to evaluate absolute bioavailability will be done separately

(ie, SC 2 × 1-mL versus IV and SC 1 × 2-mL versus IV). The primary analysis will be considered as that including SC 1 × 2-mL.

Where possible, a single linear model with contrasts to test the different objectives will be used.

Additional analyses may be conducted if they are deemed appropriate.

2. Schedule of Activities

Study Schedule Protocol I6T-MC-AMAL

| Study Day | Screening ≤ 28 days | -1 | 1 | 2 | 4 ±1d | 8 ±1d | 11 ^a ±2d | 15 ±2d | 22 ±2d | 29 ±2d | 43 ±2d | 57 ±3d | 71 ±3d | 85 ±3d | FU/ED ^d | Comment |
|--|------------------------|----|---|----|----------|----------|------------------------|-----------|-----------|-----------|-----------|-----------|-----------|-----------|--------------------|---|
| Informed consent (written) | X | | | | | | | | | | | | | | | |
| Review / confirm inclusion/exclusion criteria | X | X | | | | | | | | | | | | | | Any time prior to dosing |
| Admission to CRU | | X | | | | | | | | | | | | | | |
| Discharge from CRU | | | | X | | | | | | | | | | | | |
| Medical history | X | | | | | | | | | | | | | | | |
| Outpatient visit | X | | | | X | X | X | X | X | X | X | X | X | X | X | |
| Weight / height | X | | | | | | | | | X | | | | X | X | Height at screening only. |

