| 
Secondary
 
To evaluate the relative bioavailability of LY3074828 extemporaneously prepared as the test formulation when the same volume is administered to healthy subjects by SC injection using a single injection (1 × 2-mL) and 2 injections (2 × 1-mL).
 
To evaluate the absolute bioavailability of LY3074828 extemporaneously prepared as the test formulation when administered to healthy subjects by SC injection compared to intravenous (IV) infusion.
 
To assess the impact of Drug Product formulation changes and number of injections on tolerability of LY3074828.
 | 
SC 2 × 1-mL versus SC 1 × 2-mL of test formulation.
 
The ratio of geometric least squares means between the SC 2 × 1-mL and SC 1 × 2-mL injections will be calculated for key PK parameters of LY3074828.
 
Primary endpoints will be AUC(0-∞) and AUC(0-t_{last}).
 
The secondary endpoints will be C_{max} and t_{max}.
 
SC 2 × 1-mL versus IV; SC 1 × 2-mL versus IV.
 
The ratio of geometric least squares means of the formulations (SC/IV) will be calculated for AUC(0-∞).
 
All treatments.
 
Incidence of treatment-emergent adverse events (TEAEs).
 
Incidence of treatment-emergent anti-drug antibodies (TE-ADAs).
 |

5. Study Design

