10.1. Sample Size Determination

A total of 72 subjects will be enrolled to ensure that approximately 64 subjects complete the study (16 completers per treatment). The estimated total variability (coefficient of variation) in AUC from time zero to infinity (AUC[0-∞]), AUC from time zero to time t , where t is the last sample with a measurable concentration (AUC[0- t_{last}]), and maximum observed drug concentration (C_{max}) was 49%, 49%, and 23%, respectively, in Study AMAA following a single SC dose of 120 mg LY3074828. The coefficient of variation of 49% was used for precision estimates and is assumed for all treatment arms. A sample size of 64 subjects will provide a precision of approximately 28% for the geometric means ratio in AUC(0-∞), AUC(0- t_{last}), and C_{max} of reference to test in log scale. That is, there is a 90% probability that the half-length of the 90% confidence interval (CI) of the geometric means ratio in log scale is not larger than 28%.

Subjects who are randomized but not administered treatment may be replaced to ensure that approximately 64 subjects may complete the study.

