9.3.2 Pharmacokinetic Statistical Methodology

Log-transformed C_{\max} , $AUC(0-\infty)$, and $AUC(0-t_{\text{last}})$ estimates will be evaluated in a linear fixed-effect model with a fixed effect for formulation. Whether injection site leakage occurred (yes/no) may also be included in the model as a covariate if leakage occurs frequently. Furthermore, if this is found to be significant, the amount of leakage will also be added to the model. The formulation differences will be back-transformed to present the ratios of geometric least squares means and the corresponding 90% CI.

A single linear model with contrasts will be used for all of the following comparisons:

- Relative bioavailability of formulations: Test SC 2 \times 1-mL versus Reference

- Relative bioavailability of number of injections: Test SC $2 \times 1\text{-mL}$ versus Test SC $1 \times 2\text{-mL}$

If the number of injections is not observed to have an effect based on the above analysis, the following comparison will evaluate absolute bioavailability (on $\text{AUC}[0-\infty]$, and $\text{AUC}[0-t_{\text{last}}]$ only):

- Test SC (combined data from SC $2 \times 1\text{-mL}$ and SC $1 \times 2\text{-mL}$) versus Test IV

If the number of injections is observed to have an effect, analyses to evaluate absolute bioavailability will be done separately:

- Test SC $1 \times 2\text{-mL}$ versus Test IV
- Test SC $2 \times 1\text{-mL}$ versus Test IV

If the number of injections is observed to have an effect, the primary analysis of absolute bioavailability will be considered as that including SC $1 \times 2\text{-mL}$.

Example SAS code:

```
proc mixed data=pk;
  by parameter;
  class formulation ISLoccur;
  model log_pk = formulation ISLoccur ISLamount / residual ddfm=kr;
  lsmeans formulation / alpha=0.1 cl pdiff;
  ods output lsmeans=lsmeans;
  ods output diffs=diffs;
run;
```

The t_{max} will be analyzed using a Wilcoxon rank sum test for the relative bioavailability comparisons. Estimates of the median difference, 90% CIs, and p-values from the Wilcoxon rank sum test will be calculated.

Additional analyses may be conducted if they are deemed appropriate.

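### The endpoint tables promise SC 2 × 1-mL/IV and SC 1 × 2-mL/IV ratios in every case, but the analysis text and SAP plan them only if an undefined injection-number effect is observed (minor)

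*Protocol*

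**What the plan says.** **Endpoint tables.** Table AMAL.1 (Protocol Section 4) gives the absolute-bioavailability comparisons as "SC 2 × 1-mL versus IV; SC 1 × 2-mL versus IV" and commits to an SC/IV ratio of geometric least squares means for AUC(0-∞). The synopsis table lists the same two comparisons. Neither table attaches a condition.

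**Protocol analysis text.** Section 10.3.2.2, and the synopsis in near-identical words, makes the comparisons conditional. "If the number of injections is not observed to have an effect based on the analyses described above, data from SC" opens the rule that merges both test SC arms, and the merged analysis is primary. The separate analyses appear only in the other branch, where "The primary analysis will be considered as that including SC 1 × 2-mL". The model is described with a two-level factor: "The model will contain formulation (SC or IV) as a fixed effect". The text then prefers, where possible, a single linear model with contrasts.

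**SAP.** Section 9.3.2 keeps the same trigger: "If the number of injections is not observed to have an effect based on the above analysis, the following comparison will evaluate absolute bioavailability". The one comparison listed under it is combined SC against Test IV. The example code has the line "lsmeans formulation / alpha=0.1 cl pdiff" and no ESTIMATE or CONTRAST statement. SAP Section 11 records no changes from the protocol analyses.

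**Trigger.** The analyses referred to cover Cmax, both AUCs and tmax. Protocol 10.3.2.1 ranks the AUCs first ("The primary parameters for analysis will be" AUC(0-∞) and AUC(0-t_last)). No text ties either AUC to the switch or gives a level, margin or CI rule.

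**The concern.** A team that follows the SAP literally in the no-effect branch would leave two listed endpoint comparisons unreported. Whether that happens depends on a judgement about an effect for which no criterion is written, in an open-label study whose team may look at data while the trial runs.

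The two SC arms are compared with 16 completers each and an assumed CV of 49%. Failing to see a difference is therefore weak evidence that there is none. If the presentations do differ, the pooled ratio sits between them and describes neither. The plan itself shows that the presentation matters, since it names SC 1 × 2-mL as primary once an effect is seen. What is at stake is a complete and clearly defined report of F for each presentation. No pass/fail decision depends on it.

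**Working it through.** **Inputs.** The AUC CV is 49% in every arm (Protocol 10.1: the variability for AUC(0-∞), AUC(0-t_last) and Cmax "was 49%, 49%, and 23%, respectively, in Study AMAA following a single SC dose of 120 mg LY3074828"). There are 16 completers per arm in four arms, so the residual df are 4 × 16 − 4 = 60. The true 1 × 2/2 × 1 AUC ratio r is not in the documents and is shown as a range. The trigger is also undefined; the main assumption is that an effect is observed when the 90% CI (or 95% CI) for the ratio excludes 1.

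**Step 1: the plan's own precision figure.** σ = √ln(1 + 0.49²) = 0.4639. The 90% CI log half-width for two arms of 16 is t × σ × √(2/16):
- 30 df (two arms only): 0.278
- 60 df (four-arm model): 1.671 × 0.4639 × 0.3536 = 0.274

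The stated 28% is thus reproduced as the half-width at the assumed CV. It is not reproduced as a bound held with 90% probability, which would be 0.322 (30 df) or 0.305 (60 df). That is a separate matter, and nothing below depends on it.

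**Step 2: precision of the SC/IV ratios.**
- Each SC arm against IV: 0.274, a CI factor of e^0.274 = 1.315.
- SC average against IV: 1.671 × 0.4639 × √(1/32 + 1/16) = 0.237, a factor of 1.268.

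The listed ratios can therefore be estimated at about the planned precision with no extra subjects.

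**Step 3: what the pooled ratio estimates.** With equal arms it targets √(F(1 × 2) × F(2 × 1)). Relative to F(1 × 2) this is 1/√r, and relative to F(2 × 1) it is √r. At r = 0.80 these are 1.118 and 0.894.

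**Step 4: how often the trial would pool** (noncentral t, confirmed by simulation of 1,000,000 trials per ratio).

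| True r | Pools, 90% CI rule | Pools, 95% CI rule | Pooled ÷ F(1 × 2) | Pooled ÷ F(2 × 1) |
|---|---|---|---|---|
| 1.00 | 0.90 | 0.95 | 1.000 | 1.000 |
| 0.90 | 0.83 | 0.90 | 1.054 | 0.949 |
| 0.80 | 0.62 | 0.73 | 1.118 | 0.894 |
| 0.70 | 0.31 | 0.43 | 1.195 | 0.837 |

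Other readings of the trigger change the picture sharply. If no effect means a point estimate within 0.80–1.25, pooling occurs with probability 0.83 at r = 1.00 and 0.50 at r = 0.80. If it means a 90% CI inside 0.80–1.25, the probabilities are 0.001 and about 0.

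**Step 5: coverage.** Among trials that pool, the pooled 90% CI covers the SC average in 90% to 91% at every ratio examined. With equal arms, the SC average is independent of the SC difference on which the switch is made, so selection hardly disturbs it. Scoring each branch against its own target (SC average if pooled, F(1 × 2) if separate), coverage over both branches is 89% to 91% for r from 0.70 to 1.25.

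**The case against.** **The two texts can be read together.** The tables say which ratios are calculated, and 10.3.2.2 says which is primary; calling one analysis primary implies that others exist. This softens the mismatch but does not remove it, because SAP 9.3.2 lists only the combined comparison in the no-effect branch. The clause allowing additional analyses permits the arm-specific ratios without committing to them.

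**Little information is lost.** The 2 × 1 versus 1 × 2 ratio is always reported with its CI, and SAP Section 6 lists the arms as separate treatments, so arm-level summaries may well appear. The TFL shells were not available. This stands and limits the consequence.

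**A reader might infer that the switch makes the inference invalid.** Scored against F(1 × 2), the reported primary CI covers only 82% to 83% at r = 0.80, and 80% among pooled trials. That holds only if F(1 × 2) is taken as the target throughout. The objective is worded as SC compared with IV in general, and Step 5 shows near-nominal coverage for what each branch estimates.

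**A reader might infer that SC 1 × 2-mL should be fixed as the main contrast.** The documents do not compel this. Even for F(1 × 2), the switch under the 90% CI rule has lower RMSE than a fixed contrast at r = 1.00 (0.152 against 0.164) and r = 0.90 (0.160 against 0.164), and higher at r = 0.80 (0.177). The two arms share drug product, concentration, dose and total volume, and nothing in the documents predicts a 20% difference.

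**A reader might infer that the SAP code already yields both ratios.** With a four-level formulation factor and no covariates, the pairwise differences would include them. But the example model also carries leakage occurrence and amount, which are assessed only in the two Test SC arms. If those optional terms are used and left missing elsewhere, the IV records drop out and no SC/IV ratio is printed.

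**Conclusion.** The concern holds as a mismatch between the endpoint tables and the analysis plan: two comparisons promised without condition become conditional on an undefined observation. The consequence is that the pooled ratio may be the only planned F while it estimates neither listed quantity. At an assumed r of 0.80, this would happen in 62% to 73% of trials under the CI rules, with the pooled value 12% above F(1 × 2) and 11% below F(2 × 1). At r = 0.90 the gap is about 5% either way, and at r = 1.00 it is nil. These sizes rest on the plan's CV of 49%, 16 completers per arm, and assumed values for r and the trigger.

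Severity is minor. The objective is secondary, F has no threshold, and the pooled interval is sound for the SC average.

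**What to change.** In the synopsis, Protocol 10.3.2.2 and SAP 9.3.2:

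1. State that SC 1 × 2-mL/IV and SC 2 × 1-mL/IV are reported with 90% CIs whatever the injection-number result, as Table AMAL.1 lists them. Take them from the four-arm model without leakage covariates, because leakage is not measured in the IV or Reference arms.
2. Give the equally weighted SC average against IV as a further contrast, and put its code in the SAP. With levels in the SAP Section 6 order (Reference, 2 × 1, 1 × 2, IV), the ESTIMATE coefficients are 0, 0.5, 0.5, −1.
3. If the data are still to decide which contrast is primary, base the rule on AUC(0-∞), the parameter that Table AMAL.1 names for SC/IV, with a numerical criterion set before dosing.

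**Cost.** Items 1 to 3 are wording and one line of code. They need no extra subjects and cost the pooled contrast no precision. Making SC 1 × 2-mL the fixed main contrast is optional and has a price: a log half-width of 0.274 instead of 0.237.

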10.3.3. Pharmacodynamic Analyses

Not applicable.

10.3.4. Pharmacokinetic/Pharmacodynamic Analyses

Not applicable.

10.3.5. Evaluation of Immunogenicity

The frequency of antibody formation to LY3074828 will be determined. Treatment-emergent ADAs are those that are induced or boosted by exposure to study drug, with a 4-fold increase in titer compared to baseline if ADAs were detected at baseline or a titer 2-fold greater than the minimum required dilution (1:10) if no ADAs were detected at baseline.

If a neutralization assay is performed, the frequency of neutralizing antibodies will be determined. The relationship between the presence (or absence) of antibodies and clinical parameters (AEs) will be assessed. Likewise, the relationship between the presence of antibodies and the PK parameters to LY3074828 will be assessed.

10.3.6. Interim Analyses

The Lilly study team and investigator will be unblinded. Data may be accessed and analyzed while the trial is ongoing, but no changes to the study design are planned. An assessment committee will not be formed.

Interim analysis is scheduled to occur when safety and PK data through approximately Day 57 (8 weeks postdose) become available from enrolled subjects from each treatment. The purpose of the interim analysis is to: trigger Chemistry, Manufacturing, and Control processes with

respect to LY3074828 formulation; trigger the formal bridging study; and to inform dose selection for Phase 3 first registration.

11. References

Appendix 1. Abbreviations and Definitions

| Term | Definition |
|--------------------------------|--|
| ADA | anti-drug antibody |
| AE | adverse event: Any untoward medical occurrence in a patient or clinical investigation subject administered a pharmaceutical product that does not necessarily have a causal relationship with this treatment. An AE can therefore be any unfavorable and unintended sign (including an abnormal laboratory finding), symptom, or disease temporally associated with the use of a medicinal (investigational) product, whether or not related to the medicinal (investigational) product. |
| AUC | area under the concentration versus time curve |
| AUC(0-∞) | area under the concentration versus time curve from time zero to infinity |
| AUC(0-t_{last}) | area under the concentration versus time curve from time zero to time t, where t is the last sample with a measurable concentration |
| BMI | body mass index |
| CD | Crohn's disease |
| CI | confidence interval |
| CL/F | apparent total body clearance of drug calculated after extra-vascular administration |
| C_{max} | maximum observed drug concentration |
| complaint | A complaint is any written, electronic, or oral communication that alleges deficiencies related to the identity, quality, purity, durability, reliability, safety or effectiveness, or performance of a drug or drug delivery system. |
| compliance | Adherence to all the trial-related requirements, good clinical practice (GCP) requirements, and the applicable regulatory requirements. |
| confirmation | A process used to confirm that laboratory test results meet the quality requirements defined by the laboratory generating the data and that Lilly is confident that results are accurate. Confirmation will either occur immediately after initial testing or will require that samples be held to be retested at some defined time point, depending on the steps required to obtain confirmed results. |
| CRU | clinical research unit |
| EC | Ethics Committee |
| ECG | electrocardiogram |
| eCRF | electronic case report form |
| ED | early discontinuation |
| enroll | The act of assigning a subject to a treatment. Subjects who are enrolled in the trial are those who have been assigned to a treatment. |

| | |
|-------------------------|--|
| enter | Subjects entered into a trial are those who sign the informed consent form directly or through their legally acceptable representatives. |
| GCP | good clinical practice |
| HIV | human immunodeficiency virus |
| IB | Investigator's Brochure |
| ICF | informed consent form |
| ICH | International Council for Harmonisation |
| IL-12 | interleukin-12 |
| IL-23 | interleukin-23 |
| informed consent | A process by which a subject voluntarily confirms his or her willingness to participate in a particular trial, after having been informed of all aspects of the trial that are relevant to the subject's decision to participate. Informed consent is documented by means of a written, signed, and dated informed consent form. |
| interim analysis | An interim analysis is an analysis of clinical trial data, separated into treatment groups, that is conducted before the final reporting database is created/locked. |
| investigator | A person responsible for the conduct of the clinical trial at a trial site. If a trial is conducted by a team of individuals at a trial site, the investigator is the responsible leader of the team and may be called the principal investigator. |
| IV | intravenous(ly) |
| NA | not applicable |
| open-label | A study in which there are no restrictions on knowledge of treatment allocation, therefore the investigator and the study participant are aware of the drug therapy received during the study. |
| PK | pharmacokinetic(s) |
| QTc | corrected QT |
| SAE | serious adverse event |
| SC | subcutaneous |
| screen | The act of determining if an individual meets minimum requirements to become part of a pool of potential candidates for participation in a clinical trial. |
| SUSARs | suspected unexpected serious adverse reactions |
| t_{1/2} | half-life associated with the terminal rate constant |
| TB | tuberculosis |

| | |
|------------------------|--|
| TEAE | treatment-emergent adverse event: Any untoward medical occurrence that emerges during a defined treatment period, having been absent pretreatment, or worsens relative to the pretreatment state, and does not necessarily have to have a causal relationship with this treatment. |
| TE-ADA | treatment-emergent anti-drug antibody |
| Th17 | T helper 17 |
| t_{max} | time to maximum observed drug concentration |
| VAS | Visual analog scale |
| V_{z/F} | apparent volume of distribution at steady state after extra-vascular administration |

